### **3.3 Study Design**

#### **3.3.1 Basic PRODUCE Study Design:**

This study will employ a series of individual N-of-1 trials that compare the SCD to a modified SCD using a collaborative approach between patients, parents, and their clinical team. Patients will enter the study on a usual (non-SCD) diet and will have a minimum 1-week run in period for diet planning and baseline data collection before beginning their assigned treatment. Treatment periods will be assigned in blocks of two (e.g., AB) with the goal of each patient completing two balanced treatment blocks (e.g., ABAB) where treatment 'A' represents SCD and treatment 'B' represents modified SCD. Patients will be randomized to either the SCD or modified SCD as their starting intervention and alternate between these two conditions for four 8-week treatment periods. The study design is summarized in Figure 1.

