Symptom tracking: Participants will use the Eureka N-of-1 mobile app to execute the N-of-1 protocol, track treatment periods, and track daily and weekly symptoms and disease activity. Participants and their clinician will be able to visualize the tracked data in real-time via the Eureka N-of-1 app and on the web portal. Parents of participants will always track symptoms using the mobile app. Patients  $\geq 14$  to 18 years will have the option of tracking for themselves (in addition to their parent). Patients  $< 14$  years will have parents track for them with child input. The questions to assess symptom and disease activity metrics are included in Appendix D. Participants will be asked to start tracking at the baseline visit. Patients will be asked to complete a minimum of 2 weeks of symptom tracking in the baseline period (14 daily measures, 3 weekly measures) and will be asked to continue with tracking once they initiate the N-of-1 Trial via the Eureka app.

Stool Collection: Participants will collect a home-based stool sample for fecal calprotectin analysis and biobanking for future analysis during the baseline period and the end of each treatment period. Stool specimens will be accepted as early as up to 2 weeks before the end of the treatment periods. Active participants will not be able to advance to their next treatment block until stool is collected and sent. If a patient elects to terminate a treatment condition early, they will be asked to submit a stool specimen at that time, prior to changing treatment conditions. Participants who discontinue the study after the first crossover (e.g., completion of baseline, Diet A1, and Diet B1) and terminate the protocol early may advance to the end of the study without additional stool collection. Patient instructions for stool collection are documented in Appendix E. Fecal

## USING SINGLE SUBJECT (N-OF-1) DESIGNS TO ANSWER PATIENT-IDENTIFIED RESEARCH QUESTIONS – AIM 1

calprotectin results will be made available to the clinicians as the results are returned from the lab.

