### **3.6.2 Statistical Methods**

An overview of the statistical analysis can be found below. A formal data and statistical analysis plan will be prepared as a separate document

*Analysis of Individual N-of-1 Trials:* For the first treatment period only, there will be a 1-week run-in period as the participant gradually transitions from their usual diet to the intervention diet. A gradual transition is not needed beyond the first treatment period. For the first period, we will discard the first 7 days of data including the first weekly measurement. Based on clinical experience we expect that diet effects on symptoms wash out by 1 week. Thus, for all subsequent treatment periods we will discard the first 7 days of data including the first weekly measure during each treatment period. At the end of each person's N-of-1 trial, statistical analysis will be performed to compare results on the two treatments. Each N-of-1 trial requires a separate analysis which is automated to run in the background once each trial is completed. The analysis consists of running Bayesian models that compare the average response on each of the two treatments and baseline diet. Models will incorporate the appropriate scales for the outcomes (e.g. normal distributions for continuous variables, multinomial distributions for categorical variables) and the appropriate representation of the function linking the expected outcome to the predictors (e.g., cumulative logit link for ordinal outcomes).

Results will be reported for all study measures (stool frequency, stool consistency, PROMIS Pain interference, PROMIS GI Symptoms, fecal calprotectin) to enable patients to weigh symptoms that are most important to them. For each outcome, each patient will be provided with an estimate

## USING SINGLE SUBJECT (N-OF-1) DESIGNS TO ANSWER PATIENT-IDENTIFIED RESEARCH QUESTIONS – AIM 1

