**Weekly Symptom Trackers - Patient Version**

Weight (optional)	What is your current weight taken on your home scale in pounds? [Number]																																																																																														
PROMIS Pain Interference (patient $\geq$ 14 years)	
In the past 7 days...
 
  
 	Never	Almost Never	Sometimes	Often	Almost Always	
   
 I felt angry when I had pain.						
 
 0	1	2	3	4	
 
 I had trouble doing schoolwork when I had pain.						
 
 0	1	2	3	4	
 
 I had trouble sleeping when I had pain.						
 
 0	1	2	3	4	
 
 It was hard for me to pay attention when I had pain.						
 
 0	1	2	3	4	
 
 It was hard for me to run when I had pain.						
 
 0	1	2	3	4	
 
 It was hard for me to walk one block when I had pain.						
 
 0	1	2	3	4	
 
 It was hard to have fun when I had pain.						
 
 0	1	2	3	4	
 
 It was hard to stay standing when I had pain.						
 
 0	1	2	3	4	
  
		Never	Almost Never	Sometimes	Often	Almost Always	I felt angry when I had pain.		0	1	2	3	4	I had trouble doing schoolwork when I had pain.		0	1	2	3	4	I had trouble sleeping when I had pain.		0	1	2	3	4	It was hard for me to pay attention when I had pain.		0	1	2	3	4	It was hard for me to run when I had pain.		0	1	2	3	4	It was hard for me to walk one block when I had pain.		0	1	2	3	4	It was hard to have fun when I had pain.		0	1	2	3	4	It was hard to stay standing when I had pain.		0	1	2	3	4																																

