It was hard to have fun when I had pain.																																																																																															
0	1	2	3	4																																																																																											
It was hard to stay standing when I had pain.																																																																																															
0	1	2	3	4																																																																																											
PROMIS GI Symptoms (patient $\geq$ 14 years)	
In the past 7 days...
 
My poop was loose or watery          I rushed to the bathroom to avoid an accident          I had blood in my poop          I had a stomachache
 
Each of the four items is scored as 1 (Never), 2 (Rarely), 3 (Sometimes), 4 (Often), and 5 (Always)
																																																																																														
Pediatric Ulcerative Colitis Activity Index (PUCAI) - Patient Version	
"These are questions about how your child has been feeling over the past 24 hours"
 
Question 1. How much has your stomach been hurting in the past 24 hours?
 
 
 Not at all
 
 Hurting somewhat, but I can ignore it
 
 Hurting very much; it is always on my mind
 
																																																																																														

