	
Question 2. Did you have stools containing blood over the past 24 hours?
 
 Not at all  A small amount only, in less than half of stools  Small amount with most stools  Large amount, in more than half of stools
 
Question 3. Which of the following best describes your stool over the past 24 hours?
 
 Solid  Soft (passes easily)  Watery
 
Question 4. Number of stools per 24 hours (from yesterday this time until now). Please remember that if you are having small frequent stools one after another without having left the bathroom, it counts as one stool.
 
 0-2  3-5  6-8  More than 8
 
Question 5. Did you wake up overnight because you needed to move your bowels?
 
 No  Yes
 
Question 6. How has your activity level been over the past 24 hours?
 
 I have been able to do my usual activities without a problem  Sometimes I have had to stop what I wanted to do because I was not feeling well  I have not been able to do my usual activities at all

Short Crohn's Disease Activity Index (SCDAI) – Patient Version	
These questions refer to the time period from when you awoke yesterday to when you awoke today.
 
1. Please indicate the number of liquid or soft stools that you have had (answer: open ended frequency)

	
2. Please indicate your abdominal pain level (answer choice: 0=none; 1=mild; 2=moderate; 3=severe)
 
3. Please rate your general well-being (answer choice: 0=generally well; 1= slightly under par; 2=poor; 3=very poor; 4=terrible)

--	---

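### The washout discard goes by position in the period, but the weekly PROMIS scores look back 7 days, so a kept score can describe washout days unless the first entry falls at the end of day 7

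*Combined protocol and SAP*

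**What the plan says.** Section 3.6.2 (Analysis of Individual N-of-1 Trials) gives the reason for the discard: "Based on clinical experience we expect that diet effects on symptoms wash out by 1 week". For the first diet period it says "For the first period, we will discard the first 7 days of data including the first weekly measurement". For later periods it says "we will discard the first 7 days of data including the first weekly measure during each treatment period". Section 3.3.1 has patients "alternate between these two conditions for four 8-week treatment periods".

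In Appendix D the two weekly PROMIS instruments, in the patient and parent versions, open with "In the past 7 days". The other weekly instruments look back about one day: the PUCAI asks "how your child has been feeling over the past 24 hours", and the SCDAI says "These questions refer to the time period from when you awoke yesterday to when you awoke today".

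No section states on which day of a diet period the weekly entry is made. The nearest clue is in Section 3.4 (Symptom tracking), which asks for "14 daily measures, 3 weekly measures" over a two-week baseline. Carryover modelling is mentioned only for the meta-analysis.

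**The concern.** The plan treats the first week on a new diet as unfit for analysis. It removes that week by where an entry sits in the period. A score with 7-day recall describes the week before the entry, so the two agree only for one entry day.

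Nothing ties diet switches to a weekly grid. Baseline may last 1 to 4 weeks, and the next period waits for a stool sample (Section 3.4). Patients may switch early (Section 3.5.4), and delays are expected (Section 3.5.5). Unless the app restarts its weekly clock at each switch, the first entry of a period could fall on any of days 1 to 7.

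The outcomes concerned matter. Pain interference is the measure behind the power statement in Section 3.6.1. Both PROMIS scores are reported to each patient with the probability that one diet is better, and no carryover adjustment is described for those individual reports.

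**Working it through.** **The plan's own figure.** Section 3.6.1 states 90% power for a 3-point difference with up to 60 patients at two-sided 5%, with an exception at σ_t = 5 and ρ > 0.5. It cannot be reproduced strictly, because σ_t, ρ, the within-patient SD and the number of scores used are not defined. I assumed a patient-level contrast variance of σ_t² plus the AR(1) variance of the contrast, with 4 periods of 7 kept scores. A within-patient SD of 9 and σ_t = 5 then give 90.4%, 88.5% and 87.4% at ρ = 0.5, 0.6 and 0.7. An SD of 10 gives 87.0%, 84.6% and 83.2%. The stated pattern is plausible but not confirmed. Entry timing plays no part in this calculation.

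**Day count.** Let the first weekly entry fall on day d of a period and the second on day d + 7. The first is discarded and the second kept. If an entry describes the seven days before the entry day, the discarded score covers 8 − d days of the previous diet and the kept score covers 8 − d washout days. If the entry day itself counts, both are 7 − d.

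| First entry | Entry day not counted | Entry day counted |
|---|---|---|
| d = 1 | 7 and 7 | 6 and 6 |
| d = 4 | 4 and 4 | 3 and 3 |
| d = 7 | 1 and 1 | 0 and 0 |

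The first number in each cell is previous-diet days in the discarded score; the second is washout days in the kept score. Only an entry at the end of day 7 gives zero for both.

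**Worst case for the contrast.** Take entries on days 1, 8, ..., 50 of each period. Seven scores are kept, and one of them describes the washout week. Let f be the assumed share of the previous diet's effect present in that week; the documents give no value. Place the two diets symmetrically about a midpoint, with the usual diet at that midpoint (a neutral baseline).

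- Periods 2 to 4: the washout score carries 1 − 2f of the current diet's deviation, so the period mean keeps (6 + 1 − 2f)/7 = 1 − 2f/7.
- Period 1: the washout score carries 1 − f, so the period mean keeps (6 + 1 − f)/7 = 1 − f/7.
- Whole trial: [(1 − f/7) + 3(1 − 2f/7)]/4 = 1 − f/4.

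| f | Contrast kept | True 3 points estimated as |
|---|---|---|
| 0 | 100% | 3.00 |
| 0.25 | 94% | 2.81 |
| 0.5 | 88% | 2.63 |
| 1 | 75% | 2.25 |

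Other treatments of period 1 bracket these values. If only periods 2 to 4 are affected, 1 − 3f/14 gives 2.84, 2.68 and 2.36 for f = 0.25, 0.5 and 1. If period 1 is treated like the others, 1 − 2f/7 gives 2.79, 2.57 and 2.14.

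**Partial overlap.** With k washout days in the kept score, and f averaged over those days, the contrast keeps 1 − (k/7)(f/4). For d = 4 and k = 4 this is 1 − f/7, or 96%, 93% and 86% for the same three values of f. The overlapping days are the last ones of the washout week, where carryover should be smallest.

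**Power illustration.** Suppose power were exactly 90% without dilution, and let r be the share kept. Power is then Φ(3.24r − 1.96), or about 86%, 81% and 68% for r = 0.9375, 0.875 and 0.75. This shows sensitivity only.

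**The case against.** A reader might infer from the three weekly measures in a two-week baseline that entries fall on days 0, 7 and 14, that each diet period likewise opens with an entry on day 0, and that the day-7 score is therefore the first one kept, so that the rule fails. The documents do not support this, for three reasons.

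- Section 3.4 counts the closing entry of the two weeks to baseline, the condition just ending. Carried forward, a switch-day score belongs to the outgoing diet. The first weekly measure of the new period is then day 7, which is discarded as intended.
- Section 3.4 starts tracking at the baseline visit, so the extra baseline entry may simply be that one-off start. Nothing says that a new opening entry is made at each switch.
- If the new diet's days are numbered from 1, day 7 is among the first seven days of data and is discarded on that ground too.

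Section 3.6.2 also describes itself as an overview and announces a separate formal analysis plan, which could settle the date rule. And f = 1 is extreme beside the plan's own expectation of washout within a week.

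All of this stands. It removes the claim of a demonstrated error. It does not remove the dependence on an entry day that the documents leave open. The baseline clue assumes a two-week window, while baseline may last 1 to 4 weeks and later switches can move. The planned carryover models do not cover the individual reports.

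**Conclusion.** The concern holds in a limited form. The discard rule matches the intended washout for the two PROMIS scores only when the first weekly entry falls at the end of day 7 of each period. That timing is consistent with the documents but not stated in them.

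If entries fall earlier, one kept score per period contains washout days and as many previous-diet days are lost with the discarded score. The bias is towards no difference between the diets. It ranges from zero to a worst case in which the contrast keeps 94%, 88% or 75% of its size for f = 0.25, 0.5 or 1. Those figures rest on a day-1 entry schedule, a neutral baseline and assumed values of f. If the usual diet is not midway between the two diets, the period-1 part can shift a single patient's contrast either way, depending on the starting diet. Under 1:1 randomisation of the starting diet that part balances on average across patients.

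The daily stool items and the 24-hour PUCAI and SCDAI are not affected in this way. A reader might also take the power illustration as showing that the 90% in Section 3.6.1 is wrong. It does not: that figure lacks the inputs for a strict check, and the dilution depends on timing that may not occur. This is a minor point, worth settling because it is nearly free.

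**What to change.** In Section 3.6.2, define the discard for PROMIS Pain Interference and GI Symptoms by recall window. Drop any score whose 7-day recall includes any of days 1 to 7 of the new diet. Assign a score entered on the switch day, before the new diet starts, to the diet just finished (or to baseline, at the first switch). Apply the same rule in the automated individual analyses and in the meta-analysis.

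The cost is one sentence in the plan and one date rule in the code, with no new data and no added burden on participants. The only downside arises when entries are off-grid, where one more partly contaminated score is lost. With first entry on day 4, for example, six clean scores remain per period instead of seven scores of which one includes four washout days. If the app already scores at the end of each diet week, nothing changes.

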**Figure 1**

By completing an N-of-1 study, each individual will have a personalized answer regarding the comparative effectiveness between a highly restrictive diet (SCD) and a more broadly sustainable middle ground option (modified SCD) as compared to their baseline diet. In addition, we will aggregate the results of the completed N-of-1 trials across all patients to estimate the population level comparative effectiveness of these dietary treatments and the effectiveness of each compared to a typical, non-SCD, diet. As there is uncertainty regarding whether the sequencing of the intervention is important (e.g., whether patients must initiate a full SCD diet before modifying the diet to be less restrictive), we opted to randomize the initial treatment to be able to examine whether effects differ based on the initial diet type. Although using an ABAB/BABA design without randomization of treatment periods may result in patients anticipating their next intervention period, we do not believe this will result in increased dropout rates or failure to complete all treatment periods because patients and parent stakeholders expressed that they are interested in testing both diets—those who improve on SCD will be interested in determining whether they can maintain improvements on the modified SCD and those who improved on the liberal SCD will be interested in determining whether they can achieve greater improvements on a more strict SCD. The rationale for the duration of each treatment period (8-weeks) was based on the concern that patients would be unlikely to stay on a diet for more than 8 weeks if they did not observe a benefit and based on information from *Breaking the Vicious Cycle* and preliminary studies from research co-investigators indicating the symptoms improve within ~1 month and markers of inflammation by 2 months.

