## **3.6 Statistical Plan**

### **3.6.1 Sample Size Determination**

The primary goal of Aim 1 is to determine effectiveness of the SCD vs. modified SCD vs. usual diet for an *individual* patient. Because the focus is on the immediate decision of which treatment to select, or if the treatments were different than the patient's usual diet, it is not necessary to protect against a false-positive decision as in standard hypothesis tests used in clinical trials; thus sample size calculations are not recommended for individual N-of-1 trials. For obtaining an estimate of the population average effects of the SCD vs. modified SCD on improving symptoms, a total of up to 60 patients will participate in the two- treatment crossover study. Using the weekly PROMIS pain interference T-score measure (standardized mean of 50 and standard deviation of 10) and incorporating aspects of the design related to the number of planned crossovers, washout periods, and autocorrelation from repeated measures, we will have 90% power with a two-sided 5% alpha to detect a mean difference of 3 points between groups which corresponds to the minimally important difference on the PROMIS measures, except in the case when  $\sigma_t = 5$  and  $\rho > 0.5$  when the minimal detectable difference is above 3 to obtain 90% (but not 80% power).

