of the (1) difference in efficacy between the two diets; and (2) probability that each treatment is better than the other; as well as the (3) difference in efficacy between each diet and the baseline level; and (4) probability that each treatment is better than the baseline. Results will be portrayed numerically and graphically. We will develop educational materials to aid patients and clinicians in interpretation (Appendix B). Posterior probabilities of outcomes will be calculated using an interface that incorporates open-source R software interfacing through Rjags with open-source JAGS software. The R code creates the Bayesian model, loads the stored data and chooses intelligent starting values that are then fed into JAGS to return the Markov chain Monte Carlo (MCMC) simulations of the joint posterior distribution. The R package will accept input from the Eureka platform to construct models and return results back to Eureka for display.

Statistical analyses will be completed and patients will be given results of their individual N-of-1 studies if they complete at least one paired treatment period and there is enough data in both treatment periods to perform valid statistical analysis.

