**Meta-Analysis of N-of-1 Trials:** The collection of individual N-of-1 trials can be thought of as a set of studies whose results can be combined as in a meta-analysis. The data can be considered as a multilevel structure in which a set of patients is studied with each patient having a set of measurements. Standard multilevel mixed model methods will be used to estimate the average effect and variance within and across patients. Across patient values estimate the average effect in the population of patients studied, while the within-patient estimates describe an improved estimate of each patient's true effect assuming exchangeability across patients. We will fit these models using a Bayesian multilevel model with non-informative priors in order to obtain posterior distributions of the within and between effect sizes. We will then compare the multilevel patient estimates with those from the patient's data alone in order to determine how much the effects change and how much additional precision these estimates gain. We will also include between-patient covariates to account for variability and to test for heterogeneity of treatment effects (HTE). We hypothesize that HTE may exist based on age, sex, disease (CD or UC/IC), disease activity (mild or moderate), maintenance medication use, disease location, and disease type (inflammatory or penetrating). The model will include the baseline levels of the outcomes which will enable estimates of the effect of the study diets relative to the unrestricted diet. We will also fit models that adjust for trends over time and account for correlation and carryover. Analyses will use the appropriate probability distribution and link function for the outcome variable type (e.g. normal distributions for continuous outcomes and ordinal logistic regression with a cumulative logit link for scales).

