## **Appendix E: Patient Handout Instructions for Stool Collection**

**See Separate Document**

**Appendix F: 3-day Diet Recall Questions**  
**See Attached**

## Appendix G: N-of-1 Trial Results Display

iii. Text with each gauge

- c. Chance that SCD is Better than your Usual Diet
  - a. Text: You have a [X]% chance that you showed improvement in your stool frequency and a [X]% chance your stool frequency got worse.
  - d. Chance that the Modified SCD is Better than your Usual Diet
    - a. Text: You have a [X]% chance that you showed improvement in your stool frequency and a [X]% chance your stool frequency got worse.
2. Chance that the SCD is Better than the Modified SCD
  - a. Text: There is a [X]% chance that your stool frequency was better on the SCD and a [X]% chance that it was better on the Modified SCD.

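### Each diet versus usual diet is an uncontrolled before-after change, yet the plan reports it as efficacy or effectiveness

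*Combined protocol and SAP*

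**What the plan says.** On the design, section 3.3.1 states: "Patients will enter the study on a usual (non-SCD) diet". Patients then "alternate between these two conditions for four 8-week treatment periods". Section 3.4 (Baseline evaluation) sets the baseline period at 1 to 4 weeks and randomises only which study diet comes first. Usual diet does not return.

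On the claims made against usual diet:

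- Section 3.3.1, in the text at Figure 1, promises population estimates of "the effectiveness of each compared to a typical, non-SCD, diet".
- Section 3.6.1 gives the primary goal as to "determine effectiveness of the SCD vs. modified SCD vs. usual diet" for an individual patient. The objective in sections 2.2 and 3.2 compares only SCD with modified SCD.
- Section 3.6.2 (individual trials) lists as items (3) and (4) the "difference in efficacy between each diet and the baseline level" and the "probability that each treatment is better than the baseline".
- Section 3.6.2 (meta-analysis) says that including baseline levels allows "estimates of the effect of the study diets relative to the unrestricted diet".
- Appendix G shows families a gauge headed "Chance that SCD is Better than your Usual Diet", with a matching one for modified SCD.

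The individual analysis is described in 3.6.2 as a comparison of average responses, with no stated adjustment for time. Models with time trends appear only under the meta-analysis.

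**The concern.** SCD versus modified SCD rests on randomised order and repetition. Diet versus usual diet has neither: the comparator always comes first, in every patient, in one short block. Whatever else changes when the trial starts changes together with the diet. Candidates visible in the protocol are expectation (families know the diet, and section 3.4 measures expected benefit), added dietitian contact, and regression to the mean after entry on a raised or nearly raised laboratory marker.

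The plan nevertheless uses the same causal vocabulary for both kinds of comparison, and no passage says that one of them is non-randomised. At stake are a published claim that each diet works better than an ordinary diet, and a probability given to each family deciding whether a burdensome diet is worth keeping.

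**Working it through.** **The plan's own figure.** Section 3.6.1 gives 90% power (up to 60 patients, 3 T-score points, SD 10, two-sided 5%), for SCD versus modified SCD only. Two assumptions are needed to check it: σ_t is the between-patient SD of the diet effect, and V is the variance of a contrast of 14 against 14 weekly values with AR(1) errors over 32 weeks. Power = Φ(3/√((σ_t² + V)/60) − 1.96). This gives 92%–100% for σ_t of 0 or 3 with ρ from 0 to 0.8. For σ_t = 5 it gives 96% at ρ = 0, 87% at 0.5 and 83%–85% at 0.6–0.8. That roughly matches the stated exception; the exact ρ limit cannot be checked. No figure is given for either diet versus usual diet.

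**1. Is a shift at trial start separable from the diets?** Write the mean as β₀ + α_A·A + α_B·B + γ·time, with usual diet as reference. For five calprotectin values (baseline and four period ends, ABAB or BABA) these four columns have rank 4, so a linear trend is estimable. Add s·step, where step is 0 at baseline and 1 afterwards. Because step = A + B at every observation, rank stays 4 with 5 columns. Only α_A + s and α_B + s can be estimated. The shift s enters both diet-versus-baseline contrasts in full and cancels from α_A − α_B. More daily or weekly values do not change this.

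**2. What does the trend term cost?** Code the times 0 to 4 and assume independent errors, in residual-SD units.

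- No trend: SE = √(1 + 1/2) = 1.225.
- With trend, the slope comes from repeats within diet (sum of squares 2 + 2 = 4) and is carried back to time 0.
- Diet in periods 1 and 3 (mean time 2): √(1 + 1/2 + 2²/4) = 1.581, which is 29% larger.
- Diet in periods 2 and 4 (mean time 3): √(1 + 1/2 + 3²/4) = 1.936, which is 58% larger.

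**3. How far apart in time are the compared data?** After the first week of each period is discarded, the kept data centre 4.5 weeks into the period.

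- Diet in periods 1 and 3: (4.5 + 20.5)/2 = 12.5 weeks.
- Diet in periods 2 and 4: (12.5 + 28.5)/2 = 20.5 weeks.
- A 14-day baseline centres at −1 week, so the gaps are 13.5 and 21.5 weeks.

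An unadjusted drift of d per 8 weeks adds 13.5/8 = 1.7d and 21.5/8 = 2.7d to the two baseline contrasts. Within one patient it also adds 8/8 = 1.0d to second diet minus first, but that averages out over the two randomised orders. The baseline gap does not.

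**4. What would a family see with no diet effect?** Assume a normal outcome, a flat prior, blocks independent of each other, and lag-1 autocorrelation ρ of 0 to 0.5. Section 3.4 asks for 14 daily and 3 weekly baseline measures. Each diet keeps 2 × 49 daily or 2 × 7 weekly values. With v(n) the variance of the mean of n values, in within-person SD units, SE² = v(n_baseline) + v(n_period)/2.

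- Daily: √(1/14 + 1/98) = 0.286 at ρ = 0; √(0.194 + 0.030) = 0.473 at ρ = 0.5.
- Weekly: √(1/3 + 1/14) = 0.636 at ρ = 0; √(0.611 + 0.174) = 0.886 at ρ = 0.5.

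The displayed chance at the expected data is Φ(shift/SE):

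| Assumed shift (SD) | Daily | Weekly |
|---|---|---|
| None | 50% | 50% |
| 0.1 better | 58%–64% | 54%–56% |
| 0.3 better | 74%–85% | 63%–68% |
| 0.1 worse | 36%–42% | 44%–46% |
| 0.3 worse | 15%–26% | 32%–37% |

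The chance that SCD beats modified SCD stays at 50% under every such shift.

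**The case against.** The strongest reply is that the meta-analysis will fit models with time trends, and that repeating each diet makes a trend estimable. That is correct, and it softens the population estimate with respect to smooth drift. It reaches baseline only by extrapolation, and step 1 shows that it cannot touch a one-off shift.

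Second, the plan is partly open about the comparator. Section 3.6.2 calls it the baseline, sections 3.3.1 and 3.4 state what is randomised, and the text beneath the Appendix G headings speaks of improvement or worsening. The Appendix G extract also starts mid-list, and the separate analysis plan and the educational materials are not available, so missing caveats or time terms there cannot be inferred. The remark in 3.6.2 that the individual analysis is not adjusted for covariates explains missing-data handling and does not by itself rule out a time term. All of this stands. None of it changes the labels in the protocol, and no further document can randomise usual diet after the fact.

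Third, a reader might infer that the plan is biased in favour of the diets. The documents do not support that for symptoms, which make up four of the five primary outcomes. Section 3.5.1 sets a laboratory floor with discretion for near misses and no minimum symptom level. Section 3.5.2 caps activity scores, and a cap selects lower values: if it removed 5%–20% of patients (assumed), the rest would average 0.11 to 0.35 SD below the mean on that score, so regression would run towards worsening. For calprotectin, baseline is a fresh sample after enrolment, so some regression is over before baseline. What remains is nil if the screening value correlates equally with baseline and on-diet values.

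A reader might also infer, from the paragraph before Table 1 on obtaining missing measures from other sources, that a qualifying calprotectin could replace a missing baseline value. That paragraph reads equally well as retrieving the same measurement from another record. Section 3.4 and Table 1 fix when baseline calprotectin is taken, and nothing shows how often a fill would arise. It is not part of this point.

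**Conclusion.** The point holds as a mismatch between design and claim. Following the plan as written would report efficacy or effectiveness against usual diet, which this design cannot establish, and would place that claim in the stated primary goal.

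The structural result needs no assumed numbers: a one-off shift passes wholly into both baseline contrasts and not at all into SCD versus modified SCD. The displayed chances in step 4 are illustrations only. They depend on the assumed shift, autocorrelation, flat prior and normal scale. Stool frequency is a count and stool consistency is ordinal, and section 3.6.2 plans distributions to suit. Those figures show sensitivity, not an expected bias. The randomised comparison of the two diets and its power calculation are not called into question.

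**What to change.** - In 3.3.1, 3.6.1 and 3.6.2, call these results *uncontrolled change from the usual-diet baseline*, and keep efficacy and effectiveness wording for SCD versus modified SCD.
- In 3.6.2 (individual trials), make item (3) *change from baseline on each diet* and item (4) *probability that the outcome was better on each diet than at baseline (uncontrolled comparison)*.
- In Appendix G, change the heading to *Chance that you improved from your usual-diet baseline while on SCD*, likewise for modified SCD, and add one line saying that the change may not be due to the diet.
- In 3.6.2 (meta-analysis), state that the trend models extrapolate to baseline and do not remove a one-off shift at trial start.
- Align the primary goal in 3.6.1 with the objective in 3.2.

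The cost is wording only: no new data, visits or patients, and no change to the randomised analysis. The downside is a more modest claim against usual diet.
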